11.4. Quality assurance

To ensure compliance with GCP and all applicable regulatory requirements, Pfizer may conduct a quality assurance audit. Regulatory agencies may also conduct a regulatory inspection of this study. Such audits/inspections can occur at any time during or after completion of the study. If an audit or inspection occurs, the investigator and institution agree to allow the auditor/inspector direct access to all relevant documents and to allocate his/her time and the time of his/her staff to the auditor/inspector to discuss findings and any relevant issues.

11.5. Posting of information on publicly available clinical trial registers and publication policy

Pfizer fulfills its commitment to publicly disclose clinical trial results through posting the results of studies on www.clinicaltrials.gov (ClinicalTrials.gov), the European Clinical Trials Database (EudraCT), and/or www.Pfizer.com, and other public registries in accordance with applicable local laws/regulations.

In all cases, study results are reported by Pfizer in an objective, accurate, balanced, and complete manner and are reported regardless of the outcome of the study or the country in which the study was conducted.

www.clinicaltrials.gov

Pfizer posts clinical trial US Basic Results on www.clinicaltrials.gov for Pfizer-sponsored interventional studies conducted in patients that evaluate the safety and/or efficacy of a Pfizer product, regardless of the geographical location in which the study is conducted. US Basic Results are submitted for posting within 1 year of the primary completion date for studies in adult populations or within 6 months of the primary completion date for studies in pediatric populations.

Primary completion date is defined as the date that the final subject was examined or received an intervention for the purposes of final collection of data for the primary outcome, whether the clinical study concluded according to the prespecified protocol or was terminated.

EudraCT

Pfizer posts EU Basic Results on EudraCT for all Pfizer-sponsored interventional studies that are in scope of EU requirements. EU Basic Results are submitted for posting within 1 year of the primary completion date for studies in adult populations or within 6 months of the primary completion date for studies in pediatric populations.

www.Pfizer.com

Pfizer posts Public Disclosure Synopses (clinical study report synopses in which any data that could be used to identify individual patients has been removed) on www.Pfizer.com for Pfizer-sponsored interventional studies at the same time the US Basic Results document is posted to www.clinicaltrials.gov.

11.6. Provision of study results to investigators

Where required by applicable regulatory requirements, an investigator signatory will be identified for the approval of the study report. The investigator will be provided reasonable access to statistical tables, figures, and relevant reports and will have the opportunity to review the complete study results at a Pfizer site or other mutually-agreeable location.

Pfizer will also provide the investigator with the full summary of the study results. The investigator is encouraged to share the summary results with the study subjects, as appropriate.

Pfizer supports the exercise of academic freedom and has no objection to publication by principal investigator of the results of the study based on information collected or generated by principal investigator, whether or not the results are favorable to the Pfizer product. However, to ensure against inadvertent disclosure of confidential information or unprotected inventions, the investigator will provide Pfizer an opportunity to review any proposed publication or other type of disclosure of the results of the study (collectively, "Publication") before it is submitted or otherwise disclosed.

The investigator will provide any publication to Pfizer at least 30 days before they are submitted for publication or otherwise disclosed. If any patent action is required to protect intellectual property rights, the investigator agrees to delay the disclosure for a period not to exceed an additional 60 days.

The investigator will, on request, remove any previously undisclosed confidential information before disclosure, except for any study- or Pfizer product-related information necessary to the appropriate scientific presentation or understanding of the study results.

If the study is part of a multicenter study, the investigator agrees that the first publication is to be a joint publication covering all study sites, and that any subsequent publications by the principal investigator will reference that primary publication. However, if a joint manuscript has not been submitted for publication within 12 months of completion or termination of the study at all participating sites, the investigator is free to publish separately, subject to the other requirements of this section.

For all publications relating to the study, the institution will comply with recognized ethical standards concerning publications and authorship, including Section II - "Ethical Considerations in the Conduct and Reporting of Research" of the Uniform Requirements for Manuscripts Submitted to Biomedical Journals, <http://www.icmje.org/index.html#authorship>, established by the International Committee of Medical Journal Editors.

Publication of study results is also provided for in the clinical study agreement (CSA) between Pfizer and the institution. In this section on publications by investigators, the defined terms shall have the meanings given to them in the CSA.

If there is any conflict between the CSA and any Attachments to it, the terms of the CSA control. If there is any conflict between this protocol and the CSA, this protocol will control as to any issue regarding treatment of study subjects, and the CSA will control as to all other issues.

11.7. Reporting of Safety Issues and Serious Breaches of the Protocol or ICH GCP

In the event of any prohibition or restriction imposed (ie, clinical hold) by an applicable competent authority in any area of the world, or if the investigator is aware of any new information that might influence the evaluation of the benefits and risks of the study vaccine, Pfizer should be informed immediately.

In addition, the investigator will inform Pfizer immediately of any urgent safety measures taken by the investigator to protect the study subjects against any immediate hazard, and of any serious breaches of this protocol or of ICH GCP that the investigator becomes aware of.

12. COUNTRY SPECIFIC REQUIREMENTS

Not applicable.

APPENDIX A LABORATORY ASSAYS

The following tests will be performed using the aliquots of serum:

Functional anti-meningococcal serogroup bactericidal activity (ie, rSBA-MenA, rSBA-MenC, rSBA-MenW-135, rSBA-MenY) will be determined by a serum bactericidal assay using rabbit complement (rSBA) at Public Health England (PHE) according to the Centers for Disease Control and Prevention (CDC) protocol [[Maslanka, 1997](#)]. rSBA titres will be expressed as the reciprocal of the highest serum dilution resulting in at least 50% reduction of meningococcal colony-forming units.

- Specific antibody against tetanus toxoid will be measured by dLIA. The cut-off of the assay is 0.1 IU/mL [[McComb, 1964](#); [Newell, 1971](#)].

# Statistical Analysis Plan

MenACWY-TT-101 (C0921005)

## LIST OF ABBREVIATIONS

Abbreviation	Term
AE	adverse event
ACWY-TT	vaccinated with MenACWY-TT in Study MenACWY-TT-036
ANOVA	analysis of variance
ATP	according-to-protocol
CI	confidence interval
CSR	clinical study report
GBS	Guillain-Barré syndrome
GCP	Good Clinical Practice
GMC	geometric mean concentration
GMT	geometric mean titer
GSK	GlaxoSmithKline
MedDRA	Medical Dictionary for Regulatory Activities
MenA	N meningitidis group A
MenACWY-TT	meningococcal group ACWY tetanus toxoid conjugate
MenC	N meningitidis group C
Mencevax ® ACWY	meningococcal groups ACWY plain polysaccharide vaccine
MenPS	vaccinated with Mencevax ACWY in Study MenACWY-TT-036
MenW-135	N meningitidis group W-135
MenY	N meningitidis group Y
NOCI	new-onset chronic illness
PHE	Public Health England
RCDC	reverse cumulative distribution curve
rSBA	serum bactericidal assay using rabbit complement
SAE	serious adverse event
SAP	statistical analysis plan
SOC	system organ class
TT	tetanus toxoid
TVC	total vaccinated cohort

090177e19088d171\Approved\Approved On: 11-Mar-2019 09:48 (GMT)

**1. VERSION HISTORY**

This statistical analysis plan (SAP) for Study C0921005 (also known as MenACWY-TT-101 EXT 036: Y10) is based on protocol Amendment 3 dated 12 July 2017.

**Table 1. Summary of Major Changes in SAP Amendments**

Date	Description	Protocol Version
31-Aug-2017	Version 1	Amendment 3, 12 Jul 2017

**2. INTRODUCTION**

[figure not shown]
Subjects aged 11-17 years were vaccinated with 1 dose of either meningococcal group ACWY tetanus toxoid conjugate (MenACWY-TT) or Mencevax® ACWY in Study MenACWY-TT-036. The participants were further followed for the assessment of persistence in Study MenACWY-TT-043, and unless they withdrew their consent, they were invited for a yearly blood sample, regardless of their serostatus at the previous persistence time point, from Year 2 to Year 5 after primary vaccination. Five years after vaccination, the percentage of subjects with serum bactericidal assay using rabbit complement (rSBA) titers  $\geq 1:8$  ranged between 86.0%-97.5% in the subjects vaccinated with Nimenrix® and between 34.9%-93.0% in the subjects vaccinated with Mencevax ACWY.

The purpose of this study is to evaluate the safety and immunogenicity of a booster dose of MenACWY-TT vaccine administered 10 years after healthy subjects aged 11-17 years received either a single dose of meningococcal group ACWY tetanus toxoid conjugate (MenACWY-TT) vaccine or Mencevax ACWY. Study MenACWY-TT-036 was conducted in India, the Philippines and Taiwan. The MenACWY-TT-043 persistence study up to Year 5 after primary vaccination included only India and the Philippines. Due to Good Clinical Practice (GCP) issues in India, this booster study will only be conducted in the Philippines.

This SAP provides the detailed methodology for summaries and statistical analyses of the booster data collected in Study C0921005. Statistical analyses of persistence up to Month 120 are also described. This document may modify the plans outlined in the protocol; however, any major modifications of the primary endpoint definition or its analysis will also be reflected in a protocol amendment.

2.1. Study Design

M = month  
 BS = blood sample  
 Vacc = vaccination  
 TC = telephone contact  
 ESFU = extended safety follow-up  
 N = number of subjects in the primary total vaccinated cohort

Subjects aged 11-17 years were randomized to either MenACWY-TT (ACWY-TT) or Mencevax ACWY (MenPS) in primary study MenACWY-TT-036. Blood samples were obtained 1 month after vaccination. Subsequent blood samples were obtained at Months 24, 36, 48, and 60 in order to assess persistence of meningococcal antibodies. Immunogenicity after the initial vaccination was analyzed in the clinical study report (CSR) for Study MenACWY-TT-036. Persistence was analyzed in annual study reports for Study MenACWY-TT-043 Y2, Y3, Y4 and Y5.

Subjects will receive a booster vaccination at Month 120 in this study. The booster vaccine will be MenACWY-TT for each subject. Blood samples will be obtained before booster vaccination (Month 120) and 1 month after vaccination (Month 121). Titers before and after the booster dose will be used to assess response to booster vaccination. The vaccine groups will be ACWY-TT and MenPS, corresponding to the initial vaccination, even though all subjects will receive MenACWY-TT as the booster vaccine at Month 120.

090177e19088d171\Approved\Approved On: 11-Mar-2019 09:48 (GMT)

## 2.2. Study Objectives

Study objectives are described in terms of antibody titers to *N meningitidis* group A (MenA), *N meningitidis* group C (MenC), *N meningitidis* group W-135 (MenW-135), and *N meningitidis* group Y (MenY). Titers will be measured with a serum bactericidal assay using rabbit complement (rSBA).

### 2.2.1. Primary Objective

One month after the booster vaccination with MenACWY-TT:

- Evaluate the immunogenicity of a booster dose of MenACWY-TT conjugate vaccine in terms of the percentage of subjects with an rSBA-MenA, rSBA-MenC, rSBA-MenW-135, rSBA-MenY booster response\*.

\*Booster response to meningococcal antigens (A, C, W-135 and Y) is defined as:

- For initially seronegative subjects (prevaccination rSBA titer <1:8): rSBA antibody titer  $\geq$ 1:32 1 month after vaccination, and
- For initially seropositive subjects (prevaccination rSBA titer  $\geq$ 1:8): at least 4-fold increase in rSBA titer from prevaccination to 1 month after vaccination.

### 2.2.2. Secondary Objectives

#### Secondary immunogenicity objectives:

One month post-booster vaccination with MenACWY-TT vaccine:

- Evaluate the immunogenicity of a booster dose of MenACWY-TT conjugate vaccine with respect to the percentage of subjects with rSBA-MenA, rSBA-MenC, rSBA-MenW-135, and rSBA-MenY antibody titers  $\geq$ 1:8,  $\geq$ 1:128 and geometric mean titers (GMTs).

Before the booster vaccination and 1 month after the booster vaccination with MenACWY-TT vaccine:

- Evaluate the percentage of subjects with anti-tetanus toxoid (TT) concentrations  $\geq$ 0.1 IU/mL,  $\geq$ 1.0 IU/mL and geometric mean concentrations (GMCs).

Long-term persistence phase 10 years after primary vaccination with MenACWY-TT or Mencevax ACWY in Study MenACWY-TT-036:

- Evaluate the long-term antibody persistence induced by MenACWY-TT conjugate vaccine as compared to Mencevax ACWY when administered to individuals 11-17 years

of age with respect to the percentage of subjects with rSBA-MenA, rSBA-MenC, rSBA-MenW-135, and rSBA-MenY antibody titers  $\geq 1:8$ ,  $\geq 1:128$  and GMTs.

**Secondary safety objectives:**

- Evaluate the safety and reactogenicity of a booster dose of the MenACWY-TT conjugate vaccine.
- Describe serious adverse events (SAEs) related to study vaccination and any event related to lack of vaccine efficacy (i.e. meningococcal disease) from the subject's last visit in Study MenACWY-TT-036 or in Study MenACWY-TT-043 EXT:036 Y2, 3, 4, 5.\*

\*last visit in Study MenACWY-TT-036 will only be considered for subjects who did not participate in Study MenACWY-TT-043 EXT:036 Y2, 3, 4, 5.

**3. ENDPOINTS AND BASELINE VARIABLES: DEFINITIONS AND CONVENTIONS****3.1. Primary Endpoints**

Immunogenicity with respect to the components of the investigational vaccine 1 month after booster vaccination with MenACWY-TT vaccine:

- rSBA-MenA, rSBA-MenC, rSBA-MenW-135 and rSBA-MenY booster response\*.

\*Booster response to meningococcal antigens (A, C, W-135 and Y) is defined as:

- For initially seronegative subjects (prevaccination rSBA titer  $< 1:8$ ): rSBA antibody titer  $\geq 1:32$  one month after vaccination, and
- For initially seropositive subjects (prevaccination rSBA titer  $\geq 1:8$ ): at least 4-fold increase in rSBA titers from prevaccination to 1 month after vaccination.

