1. INTRODUCTION

1.1. Background

Invasive diseases caused by *Neisseria meningitidis* are serious threats to global health. The infection rates are highly age dependent. The risk of meningococcal disease is highest in infancy, with a secondary, slightly smaller peak in late adolescence [Rosenstein, 2001]. Case-fatality rates of invasive disease are around 10% and up to 20% of patients who recover develop significant long-term sequelae [Healy, 2002]. Prevention of meningococcal disease relies on effective immunization programs. The most common serogroups are A, B, C, W-135 and Y [Harrison, 2010].

Meningococcal disease affects mostly young children with a second peak in adolescents (15-19 year age group). For those vaccinated during childhood a booster might be needed before adolescence and for those vaccinated as young adolescent's long-term antibody persistence is needed to ensure protection throughout this peak in disease incidence [Cohn, 2010]. Meningococcal vaccines are also given to travellers, including Muslim pilgrims [Mimouni, 1998; Tawfiq, 2012]. Hence there is a need to understand how long immunity persists in case of re-exposure.

It has been observed that previous meningococcal polysaccharide vaccination may influence the immune response of a meningococcal conjugate vaccine administered three years later [Keyserling, 2005; Dbaiibo, 2012a]. It is of interest to evaluate whether this phenomenon is also observed after a longer interval between the administration of the polysaccharide and the conjugate vaccine and the potential benefit of priming with a conjugate vaccine on the booster response.

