**6.1. Immunogenicity Endpoints**

**6.1.1. Primary Endpoints**

The primary endpoint is the booster vaccination response. The primary analysis for this endpoint will use the booster ATP cohort for immunogenicity. For any group, if more than 5% of subjects who have serological results are excluded from the Booster ATP cohort, a second analysis based on the booster TVC will be performed as a sensitivity analysis. Proportions and their 2-sided 95% CIs will be compiled for each meningococcal group.

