**6.3. Subset Analyses**

Not applicable.

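### Does the booster-response percentage need a breakdown by pre-booster serostatus, because the four-fold rule penalises the group with higher pre-booster titres?

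*SAP*

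**What the plan says.** Protocol 10.1 and SAP 3.1 define booster response by two rules. A subject with a pre-booster rSBA titre below 1:8 must reach at least 1:32. A subject at or above 1:8 must show "at least 4-fold increase in rSBA titers from prevaccination to 1 month after vaccination".

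For the analysis, SAP 6.1.1 states: "Proportions and their 2-sided 95% CIs will be compiled for each meningococcal group". Here a meningococcal group means a serogroup. SAP 5.2.1 and Table 4 give the same output for each vaccine group. SAP 6.3, on subset analyses, reads "Not applicable".

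Two other statements bear on the point. Protocol 1.1 names as a matter of interest "the potential benefit of priming with a conjugate vaccine on the booster response". SAP 2 gives Year 5 percentages at or above 1:8: they "ranged between 86.0%-97.5% in the subjects vaccinated with Nimenrix" and "between 34.9%-93.0% in the subjects vaccinated with Mencevax ACWY".

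**The concern.** A percentage that depends on the starting titre is reported for two groups expected to start from different places. At Year 5 at least 86.0% of conjugate recipients were seropositive, against as few as 34.9% of polysaccharide recipients for one serogroup, so the four-fold rule would fall mostly on ACWY-TT. The group with better persistence could then look like the weaker responder even with identical post-booster immunity.

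Under one set of assumptions the gap is 2 to 17 points: 73%–97% for a group 86%–97.5% seropositive, and 90%–99% for a group 34.9% seropositive. The assumptions are a post-booster GMT of 1:2048 to 1:8192 (SD 1.5 log2) and a pre-booster GMT among seropositives of 1:128 to 1:256 (SD 2 log2). Because the protocol's background raises the effect of conjugate priming, a reader could take the two primary percentages as evidence on it and reach the wrong conclusion.

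**Working it through.** **The plan's own figures.** Protocol 10.3 takes 10% as not evaluable: 200 × 0.90 = 180, made up of 150 × 0.90 = 135 and 50 × 0.90 = 45. Clopper-Pearson limits reproduce all 18 intervals in Table 17. For example, 108/135 gives 72.3–86.4 and 36/45 gives 65.4–90.4. The sample size and intervals are sound.

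**The rule.** The two parts meet at one threshold: post ≥ 4 × max(pre, 8). A pre-booster titre of 1:8 or below requires 1:32, 1:128 requires 1:512, and 1:1024 requires 1:4096. There is no jump at 1:8. The threshold rises steadily with the starting titre among seropositive subjects.

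**Size by mixture.** Let s be the proportion seropositive. Let r_pos and r_neg be response rates by serostatus, assumed equal in both groups (the documents give no values).
- Pooled response = s × r_pos + (1 − s) × r_neg.
- Gap, ACWY-TT minus MenPS = (s_A − s_M) × (r_pos − r_neg).

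The Year 5 ranges from SAP 2 stand in for Month 120.

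| s_A vs s_M | r_neg 100, r_pos 90 | r_neg 98, r_pos 80 | r_neg 95, r_pos 70 |
|---|---|---|---|
| 86.0% vs 34.9% | 91.4 vs 96.5 (−5.1) | 82.5 vs 91.7 (−9.2) | 73.5 vs 86.3 (−12.8) |
| 97.5% vs 93.0% | −0.45 | −0.8 | −1.1 |
| 86.0% vs 93.0% | +0.7 | +1.3 | +1.75 |

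For example, 0.86 × 90 + 0.14 × 100 = 91.4 and 0.349 × 90 + 0.651 × 100 = 96.5. The gap is material at the low end of the MenPS range. At the high end it is about 1 point, or it reverses.

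**Size by simulation.** One million subjects per group were given the same post-booster distribution, with pre-booster titres set to 86.0% or 34.9% seropositive. Assumptions: pre-booster SD 2 or 3 log2, post-booster SD 1.5 log2, post-booster mean 2^10 to 2^12, correlation 0 or 0.5. ACWY-TT scores 75.0%–99.8% and MenPS 97.6%–100.0%, a gap of 0.2 to 22.6 points. Within each scenario the percentage at or above 1:128 after the booster is the same in both groups.

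**Would a split at 1:8 cure it?** Take pre-booster SD 3, post-booster mean 2^11 and correlation 0. The pooled rates are 83.3% and 98.9%. Among seropositive subjects alone they are 80.6% and 96.8%, so most of the gap remains.

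The expected seronegative counts are:
- ACWY-TT: 135 × 0.025 = 3.4 to 135 × 0.14 = 18.9.
- MenPS: 45 × 0.07 = 3.2 to 45 × 0.651 = 29.3.

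With every subject responding, the exact intervals are 29.2–100 for 3/3, 82.4–100 for 19/19 and 88.1–100 for 29/29.

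**What the plan already shows.** SAP 6.1.2 and Table 5 give pre- and post-booster GMTs, percentages at or above 1:8 and 1:128, and titre tabulations for both groups. SAP 6.1.4 puts the pre- and post-booster curves of both groups in one figure per antigen. A reader will see any baseline imbalance, and can compare post-booster levels without using a fold rise.

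**The case for a change.** The best case for a change is that a descriptive label does not stop readers from comparing two adjacent primary percentages, least of all when the protocol's background raises priming. The comparison can mislead badly. In the simulated case above (pre-booster SD 3, correlation 0, MenPS post-booster mean 2^11), ACWY-TT still scores 96.8% against 98.9% when its post-booster titres are eight times higher. GMTs and curves are marginal summaries and cannot show response at a given starting titre. One extra table uses data already held, and specifying it now is better than adding it after a surprising result.

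The dependence on starting titre stands, and so does the caution against reading the pooled percentages as evidence on priming. The need to amend the plan does not:

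- Protocol 2.1 evaluates booster response separately in each study group, and Protocol 10.7 calls all analyses descriptive. The only between-group immunogenicity comparison in the visible text is Month 120 persistence (SAP Table 7). Priming appears in the background but not among the stated objectives.
- Text is redacted after Protocol 10.6.2.1, in Protocol 10.7, after SAP 5.2.1, and at SAP 6.1.3 with Table 6. A between-group or adjusted booster analysis could sit there, so it cannot be called missing.
- Pre-booster titre is itself a result of priming. Seropositive MenPS subjects at ten years are a selected group, and comparing them with seropositive ACWY-TT subjects is not a clean comparison of priming either. A stratified table invites the same misreading on smaller numbers. Finer titre categories would describe the data better, at the price of still smaller cells.

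**Conclusion.** No change is needed. The endpoint measures what it is defined to measure, the rise over each subject's own starting level, and the planned output answers the stated within-group objective. A higher starting titre does lower the score: by about 0.2 to 22.6 points at 86.0% versus 34.9% seropositive in the simulation, and by 1.1 points or less, or in the reverse direction, when MenPS is at 93.0% in the mixture calculation.

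These sizes rest on response rates, titre means, SDs and correlations that the documents do not give. They also use Year 5 seropositivity from a persistence study covering India and the Philippines, with ranges not paired by serogroup, as a stand-in for Month 120 in the Philippines alone.

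A breakdown by pre-booster titre would be a reasonable optional table in the report. It would correct no planned result, and a split at 1:8 would not remove the effect. Conclusions about priming should rest on the post-booster GMTs and the percentage at or above 1:128, both already in the plan.
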